19.	19. Dissemination of research findings 39		
20.). References		

2. Glossary

Linear growth faltering / short stature / stunting

Children are defined as having short stature, otherwise known as linear growth faltering or stunting, if their height-for-age is more than two standard deviations below the population median height.

Linear growth faltering also encompasses reduced growth velocity, which is defined as a growth velocity of less than the 10th percentile, or the growth curve crossing 2 SD lines or centiles on a growth chart.

ASQ-3

Ages and Stages Questionnaire, third edition. Standard instrument used in the Healthy Child Programme to assess early child development in children aged one month to 5 and a half years.

GMDS

Griffiths Mental Development Scale. Development measure administered by child psychologists.

NCMP

National Child Measurement Programme.

3. Signature page

CI Agreement			
The study, as detailed within this Research Protocol, will be conducted in accordance with the principles of GCP, the UK Policy Framework for Health and Social Care Research, and the Declaration of Helsinki and any other applicable regulations. I delegate responsibility for the statistical analysis and oversight to a qualified statistician (see declaration below).			
CI name:	[name]		
	1		
Signature:			
Date:	9 Th September 2022		
Statistician's Agreement			
The study as detailed within this research protocol will be conducted in accordance with the current UK Policy Framework for Health and Social Care Research, the World Medical Association Declaration of Helsinki (1996), Principles of ICH E6-GCP, ICH E9 - Statistical principles for Clinical Trials and ICH E10 - Choice of Control Groups.			
	statistical work in this protocol is accurate and take alysis and oversight in this study.		
Statistician's name:	[name]		
Signature:			
Date:	9 th September 2022		

4. Summary and synopsis

Short title	Child growth in east London			
Methodology	Pilot growth screening programme of 630 children recruited from Tower Hamlets, East London			
	The overarching objective of this grant is to detect linear growth failure early in childhood by employing an automated growth screening algorithm for pre-school age children. The screening algorithm will be created using national data and piloted for feasibility and acceptability in Tower Hamlets, East London. We have two interlinked aims, with the following			
	hypotheses: Aim 1: Pilot an automated growth screening algorithm in a cohort of 630 children in east London.			
	Hypothesis 1 : Health visitor monitoring of child height using an automated growth-screening algorithm is feasible and is acceptable to health visitors and caregivers.			
Objectives / aims	Hypothesis 2: Referral of children to a paediatric growth clinic has high uptake and identifies growth problems in pre-school age children.			
	Hypothesis 3: An additional height measurement by a health visitor or at the child's preschool booster immunisation appointment at their GP practice is feasible and acceptable.			
	Hypothesis 4: Linkage of children's health visitor data to their height measurement as part of the NCMP is feasible and is acceptable to caregivers.			
	Hypothesis 5: A smartphone app is feasible and acceptable for caregivers to use to measure their children's height at pre-school age, and there is acceptable inter-test variability between the smartphone measurement and the clinician measurement with a stadiometer.			

	Aim 2: Generate pilot data to investigate the best	
	indicators to detect poor school readiness and	
	developmental problems in early childhood.	
	Hypothesis 1 : The addition of growth and development data to other environmental and socioeconomic variables (including Index of Multiple Deprivation) increases the pick-up rate of children at risk of poor school readiness and/or children with delayed development.	
	Hypothesis 2: There is strong correlation between the existing measurement of child development in pre-school age children (ASQ-3) and a gold standard developmental assessment by a child psychologist.	
	We will enrol a cohort of 630 children from Tower	
Number of	Hamlets, East London into a pilot screening programme at age 2-2.5 years.	
participants		
	A clinical sub-study of 200 children with confirmed	
	diagnosis of a growth disorder will also be analysed.	
	Aims 1 and 2 (630 children recruited).	
	Inclusion criteria:	
	Children aged 2-2.5 years, who live in Tower Hamlets and whose caregiver(s) are willing to provide written informed consent.	
	. Exclusion criteria: Children will be excluded if:	
Inclusion and exclusion criteria	• The caregiver does not provide written informed consent.	
	 The child is not able to stand for an accurate height measurement. 	
	Clinical sub-study (200 children)	
	Inclusion criteria:	

We estimate in this pilot study that 12 children will be referred for investigations (based on referral of 2% children with the poorest growth) and that 30-40% of these investigated in clinic will have an underlying medical disorder identified (n=4-5) based on the published literature. This pilot study is not designed to evaluate whether the age at diagnosis is significantly reduced using an automated screening approach; rather, our pilot data will inform feasibility and acceptability for a larger NIHR grant application to test the screening programme at scale with a primary outcome of age at diagnosis of medical disorders.
We will also investigate the inter-test agreement between the heights measured by caregivers using a smartphone app and heights measured by health professionals using a stadiometer.
Aim 2
Aim 2 of the pilot study will generate pilot data to investigate the best indicators to detect poor school readiness and/or developmental problems in early childhood.
We will investigate whether the addition of growth and development data to other environmental and socioeconomic variables increases the pick-up rate of children at risk of poor school readiness and/or children with delayed development.
Growth will be assessed using three height measurements as described above and development assessed as part of standard care by a Health Visitor and practice nurse.
As part of routine care, each child's development will be assessed using both the caregiver and health visitor components of the ASQ-3. Following the 2.0-2.5 year contact, a random sample of 150 children will also be invited to enrol in a sub-study to generate pilot data to investigate the correlation between the ASQ-3 and development assessed by a child psychologist using a

	Gold Standard development battery, the Griffiths Mental Development Scale (GMDS). The GMDS will be used to measure gross motor, fine motor, social, language, visual-spatial and practical reasoning skills. These data will inform a larger NIHR grant application to test the sensitivity of the parental and health visitor components of the ASQ-3.
	We will use the data to conduct analyses to test the hypothesis that linear growth failure either alone or in combination with additional factors identifies children with reduced neurodevelopment, who are therefore at risk of poor school attainment.
Study duration	3 years

5. Introduction

Poor growth in childhood can be due to underlying medical causes or socioeconomic disadvantage.⁶ In low- and middle-income countries, poor linear growth (or stunting) affects almost one-quarter of children under 5 years.⁷ The prevalence of stunting in high-income countries is less well described and may be clustered sub-nationally in areas of disadvantage. A report in 2017 by the Patients Association suggested there may be a hidden burden of stunting in deprived areas of the UK (including Tower Hamlets) and called for systematic mapping of childhood stunting and consideration of pre-school screening.⁸ We have analysed national data (unpublished) and confirmed clusters of high stunting prevalence in east London, particularly in Tower Hamlets, Newham and Hackney, after adjustment for ethnicity. Using longitudinal data from the Millennium Cohort Study for over 10,000 children with height measurements at ages 3, 5, 7, 11, 14 and 17 years, we have found consistent associations between stunting at age 3 and cognitive measures throughout childhood. Regression models adjusted for socio-economic variables showed a robust significant association between stunting and neurodevelopment (unpublished). We therefore believe that linear growth failure may be an important marker of disadvantage and reduced long-term potential among UK children, particularly in regions with substantial deprivation.

A screening programme may be valuable to refer children with severe growth failure to hospital for early investigation, diagnosis and management of serious medical disorders. Screening would also identify a larger group of children with poor growth but no underlying medical cause. We believe short stature in this group of children is a marker of disadvantage and vulnerability that is currently overlooked. We will therefore evaluate whether linear growth failure, either alone or in combination with other social and environmental factors, is a feasible, acceptable and useful marker to detect reduced cognitive development and/or poor school readiness; if so, height screening could enable targeted pre-school education and social interventions, which would be a novel public health approach to improving educational and economic outcomes across the life-course.

5.1. Background

Children with linear growth failure (i.e. low height-for-age or inadequate height velocity) may have an underlying medical cause. Early management of disorders such as growth hormone deficiency (GHD) improves long-term outcomes, but diagnosis is often delayed.⁹ In Finland, an automated growth-screening algorithm has been adopted nationwide, leading to a younger age at diagnosis of conditions such as GHD and Turner syndrome.¹⁰ In the UK, children are measured at ages 4-5 and 10-11 years through the National Child Measurement Programme (NCMP) and health visitors measure growth parameters – with weight often prioritised over height - as part of the

Healthy Child Programme. However, there is no systematic national programme to measure and monitor the heights of pre-school children, the systems do not effectively 'join up' data and there is no referral system for linear growth failure if it is identified by the NCMP. Moreover, the NCMP's focus is childhood obesity rather than linear growth, and the current cross-sectional approach of measuring children once on school entry and once on exit has limited utility in the detection of disorders underlying growth failure (99.4% specificity but < 30% sensitivity).

Many UK children with linear growth failure have no identified medical cause after investigations and are discharged from clinical follow-up. A child's dietary intake explains only a small proportion of stunting, and genetics do not account for all the variation in height in the first 5 years of life.¹¹ Linear growth is a sensitive marker of the overall wellbeing of a child, and impaired growth has multiple social and environmental causes. In low- and middle-income countries, stunting affects almost one-quarter of children, and is associated with higher mortality, impaired neurodevelopment, reduced educational attainment and lower adult economic productivity.¹² Whether these associations are also apparent in children living in high-income countries in the 21st century is less well studied.

We believe there are two situations in which UK children would benefit from linear growth screening. First, an algorithm with high specificity to detect children with medical disorders would lead to earlier referral, diagnosis and targeted treatment to improve clinical outcomes. Second, linear growth failure that is not explained by an underlying medical disorder may be an important marker of vulnerability that should not be ignored. Early identification of these children would ultimately enable tailored pre-school interventions to improve health, education and economic prospects across the life-course. This may be particularly important in areas such as east London where \sim 50% children are living in poverty, the highest rate in London.¹³

5.2. Rationale

Currently, children with linear growth failure are identified *ad hoc*, if at all, because there is no systematic screening programme in the UK. Several other European countries systematically monitor linear growth in pre-school children, resulting in earlier diagnosis of medical causes of short stature.¹⁴ From parent testimonials, it is apparent that there are often delays in identifying serious medical disorders such as growth hormone deficiency. Developing a screening algorithm for the UK pre-school population would be a major step towards identifying growth failure earlier.

Early identification leads to prompt and appropriate investigation, identification of potential co-morbidities and improves prognosis. Timely initiation of appropriate therapy is critical to minimise the impact of the disease process and maximise general health as well as height gain. Stunting is a sensitive marker of a child's wellbeing, health and educational potential across the life-course. If we generate pilot data

suggesting that growth and development measures in early childhood both improves the early identification of vulnerable children and increases the sensitivity of detecting poor school readiness, it will provide a strong rationale for a new public health approach to identifying vulnerable children in need of pre-school support through simple measurements. Using our algorithm, the screening process would be automated and have potential for adoption at scale.

5.3. Risks / benefits

Benefits: Children in the pilot growth screening programme will benefit from additional pre-school height measurements, parental monitoring of longitudinal growth through use of an app, and feedback of their growth trajectory, which would not usually be undertaken. A subset of 150 children will benefit from a neurodevelopmental assessment prior to school enrolment, which could help inform an Education Health and Care Plan for additional educational support if needed. Any children with substantial developmental delay will be referred for assessment through existing NHS systems. Additionally, 2-3% of children (~12 in total) with the poorest growth will be referred for medical review/investigations at the Royal London Hospital and we anticipate that 4-5 of these children will have a serious, treatable underlying disorder detected, based on previous data.^{15,16} The diagnosis of these disorders (such as growth hormone deficiency) is frequently delayed, traumatic for parents, and associated with suboptimal long-term outcomes.

Risks: We will collect sensitive data on household deprivation and social determinants of health on case report forms (CRFs). We are not able to completely de-identify CRFs because we will link the data to the follow-up assessment and (using NHS number) to the NCMP growth data held by Tower Hamlets Local Authority. However, data will be managed to ensure confidentiality as described in section 13. Research staff will undergo Good Clinical Practice and ethics training and the importance of confidentiality when reviewing sensitive clinical documents will be emphasised throughout the study. Child development assessments are potentially sensitive, because they measure cognitive performance, and can be misinterpreted or could be used to disadvantage a child. The results will be discussed in confidence with caregivers; we would seek their permission before sharing any of these findings and would only do so if it were in the best interests of child, for example to inform an Education Health and Care Plan to seek additional educational support for the child.

6. Study objectives

6.1. Primary objective

Pilot an automated growth-screening algorithm in east London.

Within the primary objective we aim to test four hypotheses:

- **1.** Health visitor monitoring of child height using an automated growth-screening algorithm is feasible and is acceptable to health visitors and caregivers.
- **2.** Referral of children to a paediatric growth clinic has high uptake and identifies growth problems in pre-school age children.
- **3.** An additional height measurement by the child's health visitor or at the preschool booster immunisation appointment at the child's GP practice is feasible and acceptable.
- **4.** Linkage of children's health visitor data to their height measurement as part of the NCMP is feasible and is acceptable to caregivers.
- **5.** A smartphone app is feasible and acceptable for caregivers to use to measure their children's height at pre-school age, and there is acceptable inter-test variability between the smartphone measurement and the clinician measurement with a stadiometer.

6.2. Secondary objective

Generate pilot data to investigate the best indicators to detect poor school readiness and/or developmental problems in early childhood.

Within the secondary objective we aim to test the following two hypotheses:

- 1. The addition of growth and development data to other environmental and socioeconomic variables (including Index of Multiple Deprivation) increases the pick-up rate of children at risk of poor school readiness and/or children with delayed development.
- 2. There is strong correlation between the existing measurement of child development in pre-school age children (ASQ-3) and a gold standard developmental assessment by a child psychologist.

6.3. Primary endpoint

• Feasibility and acceptability of the screening pilot.

We will assess feasibility using Bowen *et al.*'s '8 areas of focus':¹⁷ acceptability, demand, implementation, practicality, adaptation, integration, expansion and limitedefficacy testing. To achieve this, we will employ a mixed methods evaluation including qualitative data collection using focus groups with caregivers and health visitors as well as questionnaires distributed to all caregiver participants in the study and all health visitors involved in growth and development assessments. We will also collect quantitative data on: uptake of growth measurements; number of successful

growth and development measurements; number of referrals successfully completed (i.e. referred to child growth clinic with participant attending one clinic appointment); number of participants consenting to identification of their child's anthropometric data from NCMP; and uptake of the smartphone app.

6.4. Secondary endpoints

• Linear growth trajectory

This will be assessed by child height measurements at age 2-2.5 years, age 2.5-3.5 years, and age 4-5 years, in combination with target parental height. Parents who make use of the app will provide additional longitudinal growth measurements between age 2-5 years. All measurements will be entered into an algorithm, developed using data from two longitudinal UK cohorts (Millennium Cohort Study and Born in Bradford), which will identify children with poor linear growth based on absolute height, growth velocity and distance from target height.

• Child development at age 2-2.5 years.

This will be assessed using the ASQ-3 questionnaire and the GMDS, as described above.

7. Study population

This study will enrol a cohort of 630 children living in Tower Hamlets into a pilot screening programme at age 2.0-2.5 years and apply a growth-screening algorithm to identify children with poor growth. Children will be selected randomly from health visitor records in Tower Hamlets to ensure a representative sample, based on the inclusion and exclusion criteria outlined in section 7.1 and 7.2. We will include all children whose caregivers are willing to provide written informed consent to i) have a height/weight measurement (+/- a developmental assessment) together with a baseline questionnaire undertaken at age 2.0-2.5 years (by the health visitor) and a repeat weight/height measurement at age 2.5-3.5 years (either by the health visitor as an additional visit or by the GP surgery at the time of pre-school vaccinations); ii) undergo longitudinal growth screening by the parent using an app which measures a child's height; and iii) have the child's identifiers sent to Tower Hamlets Local Authority in order to access their weight/height measurement undertaken at school at age 4.0-5.0 years through the NCMP programme, to prove feasibility of data linkage. We will work in partnership with Tower Hamlets GP Care Group to identify a representative sample of children from the borough based on health visitor lists, to ensure we minimise bias and include even the hardest-to-reach participants.

We will also conduct a secondary analysis of a clinical sample of ~200 children with confirmed growth disorders e.g. Growth Hormone Deficiency, growth failure associated with small for gestational age and Turner syndrome (clinical sub-study).

These children are seen and managed in the paediatric endocrinology clinic at Barts NHS Trust. We will use this sample to test the growth screening algorithm and to identify optimal cut off values to maximize sensitivity and specificity. Retrospective consent will be sought from carers/parents to link the child's diagnosis code, age at diagnosis and parental height to their previously collected NCMP height measurement. When the patient is over 16 years old, consent will be sought from both the parent/carer and the patient, as parental data will also be shared.

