7.3 Clinical sub-study inclusion and exclusion criteria

Clinical sub-study children will be included in this analysis if they were part of the clinical sample identified as having a growth disorder at [name] clinic, and where consent can be obtained from the parent/carer and from the patient if the child patient is now over 16 years old.

8. Study design

We will enrol a longitudinal cohort of 630 children to an observational study in which weight and height will be measured as part of standard care by a Health Visitor in the community. Enrolment and baseline research data collection will be at age 2.0-2.5 years, which coincides with a current contact point with Health Visitors. Parental height will also be measured at this visit (or reported height recorded if measurement is not possible). Prior to the visit, parents will complete the standard pre-school developmental assessment sent to all households by the Health Visitor (Ages and Stages Questionnaire; ASQ-3), and the informed consent form will request

permission to record these data for research purposes. A subgroup of 150 children will be offered a developmental assessment by a psychologist as a gold-standard comparison with the parent-reported ASQ-3. A follow-up height measurement for all children will be conducted by the health visitor approximately 6-12 months later as part of an extra preschool visit which is to be piloted in Tower Hamlets. If this is not operational by the time the study starts, the follow-up measurements will take place at the preschool booster vaccine appointment at the child's GP surgery, which also occurs at age 3.0-3.5 years. If this measurement is missed for any reason, health visitors will attempt to measure the child at a community/ children's centre or at home on a separate occasion. Children will also have their height and weight measured as part of the existing NCMP programme at school entry (age 4-5 years). Additionally, parents will be invited to monitor their child's height through use of an app, if they own a smart phone, which can provide additional data-points between age 2-4 years.

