9.3 Informed consent

Informed consent will be taken by the study health visitor in a confidential setting (within a children's centre or the child's house) using e-consent on the REDCap database, which includes the questions on the study informed consent form (Form 4). If necessary, consent can be taken on paper using the same form and will still be considered valid. This will take place either prior to the first measurement/development assessment at age 2-2.5 years or on the day of this assessment. An electronic signature will be taken; in addition to a tick box and declaration, permitted forms of electronic signatures will include a stylus or finger drawn signature or a typed name. The health visitor will explain all study procedures, risks and benefits and confidentiality considerations. The study health visitor will explain that the project involves two assessments by health professionals, 6-12 months apart (one at the 2-2.5 year health visitor contact and one undertaken either by the GP surgery at the preschool booster immunisation appointment, or by the health visitor). In addition, as per standard care all children will have their development assessed by the health visitor using the parent-reported ASQ-3 assessment. Parents will also be invited to download a smartphone app and to measure their child's height at 3 timepoints, each time on the same day as the child's height is measured by a health professional (health visitor, GP practice nurse, school nurse). Caregivers will also be asked for consent to health visitors' collection of data on past medical history from children's primary care records and linkage of any relevant diagnoses or medications to the children's study data. It will also be made clear that there will be data linkage with the NCMP programme through Tower Hamlets Local Authority, which involves sharing identifiers (NHS number) if they are happy to provide consent for this to occur. Caregivers can opt out of this data linkage and their child can still be included in the internal study. Caregivers will be made aware that they will be provided with the child's growth measurements and a summary of their growth pattern, and that children with severe growth failure will be contacted and referred to the paediatric endocrinology service, and children with significant developmental concerns will be referred for further assessment through existing NHS referral pathways. In addition to data entry onto the NHS system, the caregivers will be made aware that their child's anthropometric and developmental data, and the parental heights will be recorded in a research database (REDCap) by the health visitor. Caregivers will be asked for consent for routine clinical data collected in the clinic (such as any diagnoses made by the endocrinologist) to be linked with the child's data in the study. [name] is a member of the study team and

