We will employ an algorithm based on previous methodology, using variables individually and in combination, after checking for co-linearity. Different cut-off values will be chosen and the proportion of the population judged to have linear growth failure estimated for each cut-off. We will then examine the detection rate for each cut-off by applying it to data from ~200 local children treated in the specialist paediatric endocrinology centre with known growth disorders e.g. Growth Hormone Deficiency (GHD), Turner Syndrome (TS) and Small for Gestational Age without catch-up growth (SGA). Consent will be obtained retrospectively from these patients and their parents/carers to link their routinely obtained clinical data (diagnosis, age at diagnosis, height and parental height) to previously height data obtained at school entry via the NCMP. To do this linkage, the hospital clinical data (and the associated NHS number or other identifiers) will be shared with NHS England. This will allow us to calculate sensitivity-and-specificity algorithm cut-offs for the detection of these conditions. This will enable a trade-off between detection rate (sensitivity) and the false positive rate (1-specificity) to be evaluated. Additionally, the time elapsed from the first abnormal screening result until the clinical diagnosis of growth hormone deficiency will be related to the cut-off values.

The outcomes for Aim 1 are age of identification of stunting (which will be reported but the study is not powered to detect age of diagnosis); feasibility of measuring children in the community; the percentage of children referred; the percentage of children found to have underlying medical conditions; and the feasibility, acceptability and inter-test variability of a smartphone app and stadiometer height measures.

The algorithm will be applied to measures collected from each child at each visit, with children who are identified by the algorithm as being in the bottom 2% for height or

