growth being referred to clinic for further investigation. The proportion of children with complete observations, including height at three time points and parental height, will be compared to the proportion of children with fewer observation points or missing parental height. Descriptive statistics will be reported: the number and percentage of children found to be stunted and their characteristics (height, gender, age, socio-demographic factors). We will also report the number of children referred to clinic, attending clinic and found to have underlying medical conditions. The age at which each condition is identified will be reported and compared to the average age at diagnosis.

Height data collected by parents using a smartphone app will be analysed. The number of parents consenting to use of the smartphone app and reporting one or more height measurements through the app will be reported. The number of time points at which parent's upload smartphone measured heights will also be reported. Inter-rater reliability between parent-measured height using the smartphone app and Health Visitor measured height using a stadiometer will be assessed using Gwet's Agreement Coefficient.¹⁹

Aim 2

All children will undergo a developmental assessment in the community, conducted by a health visitor with input from the child's parent, as part of standard care (ASQ-3 questionnaire). A subset of 150 children will, in addition, have a gold standard developmental assessment conducted by a child psychologist using the GMDS, which measures gross motor, fine motor, social, language, visual-spatial and practical reasoning skills.

Data on socioeconomic circumstances will be used to model the probability of a child's risk of developmental delay or sub-threshold delay on the ASQ-3 (n=600) and GMDS (n=150). Poor growth (assessed by the algorithm) will then be included in these models to assess whether model fit is improved, and whether poor growth contributes to the predictive power of socioeconomic variables to predict developmental delay.

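### Section 6.4 puts caregiver app heights into the growth algorithm while app agreement is still under test, and the protocol contradicts itself on app timing and on which heights the algorithm uses

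*Protocol*

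**What the plan says.** **What enters the algorithm.** Section 6.4 (Linear growth trajectory) lists the three scheduled heights and adds: "Parents who make use of the app will provide additional longitudinal growth measurements between age 2-5 years". The next sentence reads "All measurements will be entered into an algorithm, developed using data from two longitudinal UK cohorts", and the algorithm is one "which will identify children with poor linear growth based on absolute height, growth velocity and distance from target height". App heights are not excepted. Section 8 also mentions the app and then sends longitudinal heights to the algorithm whose lowest 2-3% are offered referral.

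**When the algorithm runs.** The synopsis (section 4) applies it to three time points. Section 9.4 (school entry measurement) identifies the poorest-growing 2-3% at each of the three height measurements. Section 10.2 (Aim 1) says "The algorithm will be applied to measures collected from each child at each visit".

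**When app readings are taken.** Section 6.4 has extra readings from age 2 to 5. Section 8 describes the app as something "which can provide additional data-points between age 2-4 years". Section 9.3 asks for three readings, "each time on the same day as the child's height is measured by a health professional".

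**Status of the app.** Hypothesis 5 in section 6.1 includes the claim that "there is acceptable inter-test variability between the smartphone measurement and the clinician measurement with a stadiometer". Section 10.2 tests it on this study's own data: "Inter-rater reliability between parent-measured height using the smartphone app and Health Visitor measured height using a stadiometer will be assessed", using Gwet's coefficient. No rule holds app heights back until agreement has been shown.

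**The concern.** Read as written, section 6.4 lets an instrument whose agreement is a study question help to define a secondary endpoint of the same study. The algorithm runs during the study, before the agreement result is known.

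Growth velocity is the most exposed component. It is a difference of two heights divided by a short interval, so height error is magnified. Families who use the app would also have their child's endpoint built from different data than families who do not.

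What is at stake is the meaning of two results: the linear growth endpoint, and the proportion of referred children with a medical condition. Section 10.1 judges the algorithm on that proportion among about 12 referrals. If app heights feed the algorithm, both results mix the screening method with the app's error.

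**Working it through.** **1. Passages side by side.** Same-day readings (section 9.3) add no new age to a child's trajectory, so they cannot be the extra points of sections 6.4 and 8. Those two sections also give different upper ages (5 and 4). Entering all measurements (6.4) and running the algorithm on visit measures (10.2) agree only if app readings are excluded, or if same-day app readings count as visit measures. The protocol says neither. These contradictions do not depend on any assumed app error.

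**2. The plan's own figure.** Section 10.1 gives 12 referrals, an expected yield of 35% against 5%, 5% significance and 85% power. Exact binomial, at least 3 of 12:
- P(X ≥ 3 | 0.05) = 0.0196
- P(X ≥ 3 | 0.35) = 0.849, which reproduces the 85%.

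If false flags displaced true cases among a fixed 12, P(X ≥ 3) would be 0.747 at a yield of 30%, 0.609 at 25% and 0.442 at 20%. The protocol gives no basis for choosing among these yields.

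**3. Illustration of dilution.** The documents give no app or stadiometer error, so every input here is an assumption: true velocity SD 0.9 cm/yr, stadiometer error SD 0.4 cm, interval t = 0.75 yr, normal unbiased errors, lowest 2% taken by rank, and one stadiometer height replaced by an app height.

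- Velocity error SD = √(e² + 0.4²) / t, where e is the error SD of the other height.
- Correlation with true velocity: ρ = 0.9 / √(0.9² + error SD²).
- Share of flagged children truly in the lowest 2% = Φ₂(z, z; ρ) / 0.02, where z = −2.054 and Φ₂ is the bivariate normal distribution function.

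| Other height | e (cm) | Error SD (cm/yr) | ρ | Share |
|---|---|---|---|---|
| Stadiometer | 0.4 | 0.566/0.75 = 0.754 | 0.766 | 38% |
| App | 0.5 | 0.640/0.75 = 0.854 | 0.726 | 34% |
| App | 1.0 | 1.077/0.75 = 1.436 | 0.531 | 19% |
| App | 1.5 | 1.552/0.75 = 2.070 | 0.399 | 12% |

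An app with e = 0.4 cm reproduces the first row, so replacement then costs nothing. Over 12 months the four shares are 49%, 44%, 26% and 17%.

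These are shares of children with truly low velocity. They are not diagnostic yields, and the documents do not allow one to be converted into the other.

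**The case against.** **Referral.** A reader might infer that app heights will certainly send children to clinic. The documents do not support that. Section 6.4 describes an endpoint and does not mention referral, while sections 4, 9.4 and 10.2 tie flagging to the three measurements or visits. This stands. What remains is that none of those sections excludes app readings, and section 9.3 collects app readings on the same days.

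**More flags.** A reader might also infer that app error multiplies the number of flagged children. With a velocity cut-off fixed at 2% on stadiometer pairs and the assumptions above, app error SD 1.0 cm would flag 7.7% at nine months. But sections 4, 8, 9.4 and 10.2 take a lowest 2-3% or 2%, which is a ranked share. Under ranking the count stays put and error swaps true cases for false ones. Only section 9.5, which refers any child with reduced velocity at follow-up, is looser.

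**Assumed inputs.** The app may be as precise as the stadiometer, and one that reads tall would hide poor growth rather than create false flags. Extra readings also need not replace stadiometer heights. All of this stands, and the table is therefore an illustration only.

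**Consequence.** The primary endpoint is feasibility and acceptability. The failure rule written in section 10.1 is fewer than one diagnosis. The chance of none among 12 is 0.65¹² = 0.6% at a yield of 35% and 0.75¹² = 3.2% at 25%, so that conclusion moves little. This stands; the loss falls on the yield estimate and on the power that section 10.1 claims.

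**Detail for an analysis plan.** Which heights enter each run could be left to a separate plan. Here, though, the protocol states a data rule for a named endpoint and contradicts it elsewhere.

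**Conclusion.** The point holds as an inconsistency with a possible bias. Section 6.4, as worded, admits app heights to the secondary growth endpoint before their agreement with the stadiometer is known. Other sections describe the algorithm's input and the app's timing in ways that cannot all be followed.

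The contradiction is certain from the text. The size of the bias is not: it is nil if an equally precise app reading replaces a stadiometer one. With assumed app error SD of 1.0 cm over nine months, it would halve the truly low-velocity share of flagged children (38% to 19%). Neither an inflated flag rate nor app-driven referral is established. It should be corrected before data are analysed, but it does not threaten the primary feasibility endpoint.

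**What to change.** 1. Reconcile sections 4, 6.4, 8, 9.3, 9.4, 9.5 and 10.2 on when app readings are taken and on which heights feed the algorithm, including for referral. Which heights should trigger referral is a clinical rule for the sponsor and the investigators; this review does not propose one.
2. For the analysis, state that the linear growth endpoint and the reported algorithm performance use professionally measured heights (study visits and NCMP).
3. Use the same-day app readings for the agreement analysis under hypothesis 5.
4. Rerun the algorithm offline with app heights included, as a sensitivity analysis, and report how many children change classification.

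The cost is wording; no extra data or staff are needed. The downside is that between-visit app readings would not contribute to the main growth endpoint, although they would still be used in the sensitivity run.
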